### 10.7 Procedures for missing, unused and spurious data

Analysis of the primary outcomes will be via intention to treat with data from all participants included in the analysis. Every effort will be made to follow up all participants up to the primary endpoint, however, as missing data is inevitable, we will employ statistical techniques for handling missing data for the primary outcomes. The primary negative binomial regression model will account for exposure time (person-time). Should there be other predictors of missingness not adjusted for in the primary model, a sensitivity analysis for effect of missing data will use multiple imputation, based on multivariate imputation by chained equations (MICE), under the missing at random assumption. At least 20 imputations will be performed, and the results combined using Rubin's rule.

### 10.8 Definition of populations analysed

For the primary analysis, all randomised participants who receive at least one dose of the study medication, will be analysed according to allocated treatment group regardless of adherence to the allocated treatment. This will be supplemented by analysing only the participants who would comply with their allocated intervention. Full definition and cut-off for compliance will be specified in the SAP.

For the secondary outcomes, participants will be analysed according to allocated treatment group regardless of adherence to the allocated treatment.

For the safety outcomes, all randomised participants who receive at least one dose of the study medication will be analysed according to:

- treatment received.

- allocated treatment group regardless of adherence to the allocated treatment.

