### 4.3 Primary endpoint

Number of flares over 12 months. Flare is defined as worsening of symptoms requiring increased application of TCSs as reported by participants via two weekly reminders.

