## 8 TRIAL TREATMENT AND REGIMEN

Trial participants will be allocated to either 'Proactive' or 'Reactive' treatment arm. In the 'Proactive' arm, participants will be prescribed their TCS by their treating physician twice a week for 24 months, regardless of presence of LS symptoms. In the 'Reactive' arm, participants will be allocated to use their TCS only when LS symptoms (or increase in visual signs) are present (please refer to table below for more details). The choice of TCS will be at the discretion of the treating physician. Repeat prescriptions will be obtained by participants as per the usual care.

*Table 6. Intervention vs comparator group*

Treatment group	Proactive Intervention group	Reactive Comparator group
Treatment name	Superpotent or potent topical corticosteroid	Superpotent or potent topical corticosteroid
Formulation	Cream/ointment	Cream/ointment
Dosage	1 application twice-weekly on two non-consecutive days in the absence of symptoms. If symptoms flare, apply once a day until symptoms resolve.	Only use during flare. Apply once a day until symptoms resolve.
Route of administration	Topical (application of a thin layer on affected area)	Topical (application of a thin layer on affected area)
Sourcing	Provided directly as per usual care	Provided directly as per usual care
Packaging and labelling	Topical steroid will be provided and labelled as per usual care prescription, and as required for each patient	Topical steroid will be provided and labelled as per usual care prescription, and as required for each patient

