### 10.2 Analysis of outcome measures

The reporting of the trial will be in accordance with CONSORT guidelines. A full statistical analysis plan (SAP) will be developed and agreed with the Trial Steering Committee (TSC) prior to database lock.

Appropriate descriptive statistics for the demographic and clinical outcome measures at baseline will be used to assess balance between the randomised arms at baseline. Descriptive statistics appropriate for the outcome will also be presented for all outcomes at all collected time points by treatment arm.

Primary analysis will compare the average number of flares per person-time between the treatment groups, with analysis according to the allocated treatment strategy regardless of adherence to the strategy (intention-to-treat). Negative binomial regression, adjusted for minimisation factors and incorporating exposure time (person-time), will be used to calculate the incident rate ratio and 95% confidence interval. Supplementary analyses for the primary outcomes will use per-protocol or complier average causal effect (CACE) analysis if possible to estimate the effect of the intervention among the participants who would comply with their allocated intervention. Subgroup analyses for the primary outcome will be performed according to age at randomisation (children or adult), time since last flare, and strength of prescribed TCS (potent or superpotent), by including appropriate interaction terms in the primary model, however, results will be regarded as exploratory as the trial is not powered to detect interactions. Any additional sub-groups to be explored will be pre-specified in the SAP.

Between-group comparison of secondary outcomes will be based on an appropriate regression model for the outcome (or appropriate non-parametric estimator), adjusted for the same variables as the primary analysis.

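### The one-dose condition in the primary analysis population contradicts intention to treat and selectively removes flare-free reactive participants, which biases the rate ratio towards proactive

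*Protocol*

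**What the plan says.** **Primary population.** Section 10.8 defines it as "For the primary analysis, all randomised participants who receive at least one dose of the study medication", analysed by allocated group whatever their adherence. It sets no period within which the dose must fall. The secondary-outcome population in the same section carries no dose condition.

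**Intention to treat.** Section 10.2 describes the primary comparison "with analysis according to the allocated treatment strategy regardless of adherence to the strategy (intention-to-treat"). Section 10.7 goes further: "Analysis of the primary outcomes will be via intention to treat with data from all participants included in the analysis".

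**Dosing by arm.** Inclusion criterion 2 (section 7.4.1) requires controlled, symptom-free disease at entry. For the proactive arm, Table 6 in section 8 specifies "1 application twice-weekly on two non-consecutive days in the absence of symptoms". For the reactive arm it says "Only use during flare. Apply once a day until symptoms resolve". The text above that table is slightly wider: "participants will be allocated to use their TCS only when LS symptoms (or increase in visual signs) are present".

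**Outcome.** Section 4.3: "Flare is defined as worsening of symptoms requiring increased application of TCSs as reported by participants via two weekly reminders".

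**Safety.** Section 10.8 repeats the condition: "For the safety outcomes, all randomised participants who receive at least one dose of the study medication will be analysed according to" treatment received and, separately, allocated group.

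**The concern.** In the proactive arm, whether someone takes a first dose has almost nothing to do with flares. In the reactive arm it has almost everything to do with them: a participant who follows the allocated strategy and has no flare has no reason to apply TCS. A population rule based on dosing is therefore close to a rule based on the primary outcome, and it acts that way in one arm only. It takes zero counts with full follow-up out of the comparator and leaves the matching participants in the intervention arm.

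The direction follows from the text. The retained reactive flare rate rises, and the proactive-to-reactive IRR falls. Neither the person-time offset nor adjustment for minimisation factors repairs this, because the people removed have complete exposure and a count of zero. What is at stake is type I error control and an unbiased effect estimate in the sole primary analysis, with the error favouring the hypothesis under test.

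**Working it through.** **Inputs (section 10.1).** Reactive rate 4 per year; proactive rate 3 (IRR 0.75); dispersion k = 0.34; 90% power; two-sided 0.05; 320 for analysis (160 per arm); 400 randomised (200 per arm). The survey mean and SD are 4.0 and 2.8.

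**Step 1: reproduce the plan's figure.** n per arm = (1.960√V0 + 1.282√V1)² / (ln 0.75)², where V1 = 1/4 + 1/3 + 2 × 0.34 = 1.263 and V0 = 2/3.5 + 2 × 0.34 = 1.251 (pooled null rate 3.5). The result is 159.5, so 160 per arm and 320 in total. Then 320/0.80 = 400. The plan's numbers reproduce, so the same model can be used to size the bias.

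**Step 2: share of the reactive arm with no flare.** For a negative binomial count with mean μ, P0 = (1 + kμ)^(−1/k). Dropping the zeros raises the mean to μ/(1 − P0) and multiplies the IRR by (1 − P0).

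*Dose must fall within 12 months (μ = 4, k = 0.34):*
- P0 = 2.36^(−2.941) = 0.080, about 13 of 160 or 16 of 200.
- Retained reactive mean = 4/0.920 = 4.35.
- IRR with no effect = 4/4.35 = 0.92; IRR at the design effect = 3/4.35 = 0.69.

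*Same window, dispersion from the survey SD:*
- k = (2.8² − 4)/4² = 0.24, and P0 = 1.96^(−4.167) = 0.061.
- Null IRR 0.94; design IRR 0.75 × 0.939 = 0.70.

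*A first dose in months 13 to 24 also qualifies (μ = 8 over two years, assuming the rate of 4 continues, k = 0.34):*
- P0 = 3.72^(−2.941) = 0.021.
- Retained 12-month mean = 4/0.979 = 4.09.
- Null IRR 0.98; design IRR 0.73.

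**Step 3: type I error and apparent power.** These come from simulation: at least 4,000 trials per scenario, negative binomial counts, Wald test with maximum-likelihood dispersion, full 12-month follow-up, no covariates.

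| Population analysed | Type I error, 160/arm | Type I error, 200/arm | Apparent power at 4 v 3, 160/arm |
|---|---|---|---|
| All randomised, k = 0.34 | 0.05 | 0.05 | 0.90 |
| Dosed within 12 months, k = 0.34 | 0.18 | 0.21 | 0.99 |
| Dosed within 12 months, k = 0.24 | 0.14 | 0.16 | not needed |
| Dosed within 24 months, k = 0.34 | about 0.06 | about 0.06 | 0.94 |

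In the 24-month row, individual runs lay between 0.05 and 0.07. In the 12-month rows nearly all false rejections favour proactive. The 200-per-arm column assumes that every randomised participant gives complete data; the plan expects 320 for analysis.

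**The case against.** **The protocol already states intention to treat.** Sections 10.2 and 10.7 do so, and one clause in 10.8 is the outlier. That is fair, and it is why the fault is first a contradiction. But 10.8 is the section that defines populations, and it defers only the compliance definition to the SAP. The clause cannot be passed over.

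**The size depends on an unstated window.** This stands in full. A reader might infer from the 12-month figures that type I error is certainly near 0.2. The protocol does not support that. Allocated treatment runs for 24 months (section 8), and if a first dose in the second year counts, the distortion is small. The primary endpoint is at 12 months, but nothing in the text settles which window applies.

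**No flare is not the same as no dose.** This also stands. Section 8 lets reactive participants treat visual signs, whereas a flare is a participant-reported worsening of symptoms. Some will also use TCS outside their strategy and remain in the population. If receiving a dose were read as being prescribed one, flare-free participants would not be lost at all, though the text says dose. Proactive participants who never start would be dropped too, so the removal is selective rather than strictly confined to one arm. The percentages are therefore ceilings at the stated planning values.

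**Could the rule be applied at all?** A reader might infer from section 8.4, which provides for no dispensing or accountability records, that the condition could never be checked. The protocol does not go that far: section 14.3.1 has prescriptions counted on the e-CRF, and section 8.3 has adherence asked at five visits. These are imperfect markers of a first application, but they could be used to exclude people.

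**Safety is a different matter.** A reader might tie the safety population to the IRR bias. It has no bearing on that ratio, and restricting a treatment-received safety summary to exposed participants is conventional.

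**Lower flare rates.** A reader might extrapolate to a lower reactive rate with a much larger bias. The protocol gives no such planning rate for the reactive arm. The one-year relapse figure in section 1.4 concerns patients using only emollients.

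**Conclusion.** The point holds. The population in section 10.8 conflicts with sections 10.2 and 10.7 and, applied as written, biases the primary IRR towards proactive. The direction rests only on the protocol's own dosing rules, entry criterion and flare definition.

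The size is less certain. With a 12-month window and dispersion 0.34, up to 8.0% of the reactive arm is lost, and the null IRR falls to about 0.92. A true 0.75 then reads as about 0.69, with type I error about 0.18 to 0.21 (0.14 to 0.16 at dispersion 0.24). With a 24-month window, about 2% are lost, the null IRR is about 0.98 and a true 0.75 reads as about 0.73. Type I error is then about 0.06, and no more than about 0.07. All of these assume that no flare-free reactive participant applies any TCS, so the true effect would be no larger at these planning values.

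Correction is needed even on the mild reading, because the primary population should not depend on an unstated window or on the outcome itself.

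**What to change.** In section 10.8, delete the one-dose condition from the primary population. State instead that all randomised participants are analysed by allocated strategy, whether or not any TCS was used, with exposure time as the offset. Carry the same definition into the SAP. This restores the analysis that sections 10.2 and 10.7 already describe: IRR 1.00 under no effect, type I error about 0.05 and power about 0.90 at 160 per arm.

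Separately, and of lesser weight, remove the one-dose condition from the by-allocation safety summary so that unexposed reactive participants stay in its denominator. The dosed-only summary by treatment received can stay.

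The cost is two edits in one section and whatever amendment step section 14.1 requires. No new data, visits or participants are needed.

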## 11 ADVERSE EVENTS

An adverse event is any unfavourable and unintended sign, symptom, syndrome or illness that develops or worsens during the period of observation in the study.

An AE includes:

1. Exacerbation of a pre-existing illness.
2. Increase in frequency or intensity of a pre-existing episodic event or condition.
3. Condition detected or diagnosed after medicinal product administration even though it may have been present prior to the start of the trial.
4. Continuous persistent disease or symptoms present at baseline that worsen following the start of the trial.

The interventions being evaluated in this trial are treatments that are widely available within the NHS and used in standard care for lichen sclerosus. Given the well-known safety profile of the interventions, we will adopt a targeted approach to AE reporting.

Reporting and follow-up of these targeted participant and investigator-reported complications associated with the intervention delivery will be recorded in trial e-CRFs in a structured format and do not need to be reported to the Research Ethics Committee (REC).

An AE does not include:

1. Medical or surgical procedure (e.g., surgery, endoscopy, tooth extraction, transfusion); but the condition that leads to the procedure is an AE.
2. Pre-existing disease or conditions present or detected at the start of the trial that did not worsen.
3. Situations where an untoward medical occurrence has not occurred (e.g. hospitalisations for cosmetic elective surgery, social and / or convenience admissions).
4. Disease or disorder being studied or sign or symptom associated with the disease or disorder unless more severe than expected for the participant's condition.
5. Overdose of concurrent medication without any signs or symptoms.

Although all AEs should be recorded in the medical notes, in accordance with GCP, only those AEs which are directly referred to in the e-CRF will be collected for this trial. However, where any AE event meets the criteria of an SAE (see section 11.2), it will require reporting on a SAE form by the PI or delegate.

### 11.1 Reference Safety Information:

The known side effects are events that do not require expedited reporting (providing they do not meet the criteria of an SAE), but will be collated on the e-CRFs, have been taken from the exemplar

Summary of Product Characteristics, sections 4.8 of Dermovate ointment and Elocon ointment, and are detailed in this protocol section 11.4.

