## 2.6 Known Side Effects

Known adverse reactions to TCSs include: infection, folliculitis, paraesthesia, burning sensation, contact dermatitis, skin hypopigmentation, hypertrichosis, skin striae, acneiform dermatitis, skin atrophy, pruritus and application site pain, according to the Summary of Product Characteristics (SmPC).

TCSs are used to treat a very wide range of inflammatory skin conditions, including common conditions such as eczema, psoriasis, vitiligo as well as LS. The risk of adverse effects for potent or superpotent TCSs (such as used in this trial) is modest, but it is widely acknowledged that the fear of adverse effects is usually disproportionately high, given the relative infrequency with which such adverse effects are observed. Despite the ubiquity of topical corticosteroids in dermatological therapeutic practice, there is surprisingly little evidence to quantify the risk of adverse effects accurately. Guidelines often suggest that potent/superpotent TCSs should be used only under close clinical supervision, particularly when used in children on anatomical sites where the skin is thinner and therefore more prone to adverse effects such as atrophy.

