#### **11.4 Reporting of adverse events**

Targeted adverse events will be recorded and closely monitored until resolution, stabilisation, or until it has been shown that the trial medication or treatment is not the cause.

In the PEARLS trial these targeted AEs are:

- Progression of scarring
- Pre-cancerous changes to the anatomy
- Infection (thrush and superficial bacterial infection)
- Hypersensitivity, generalised rash
- Cushing’s syndrome
- Local skin burning/skin pain and pruritus
- Allergic/contact dermatitis, erythema, rash, urticaria, local atrophic changes in the skin such as thinning, skin wrinkling, skin dryness, striae and dilatation of the superficial blood vessels (telangiectasias) may be caused by prolonged and intensive treatment with highly active corticosteroid preparations, particularly when occlusive dressings are used or when skin folds are involved.

Sites should report these events via e-CRFs.

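### Section 11.1 says the known steroid reactions are detailed in section 11.4, but five of the twelve listed in section 2.6 are not named there, and at least two have no place in it

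*Protocol*

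**What the plan says.** Four parts of the protocol bear on this point.

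- **Section 2.6** attributes this list of known topical corticosteroid reactions to the product information: "infection, folliculitis, paraesthesia, burning sensation, contact dermatitis, skin hypopigmentation, hypertrichosis, skin striae, acneiform dermatitis, skin atrophy, pruritus and application site pain". That is twelve terms.
- **Section 11.1** says that non-serious known side effects need no expedited reporting, "but will be collated on the e-CRFs, have been taken from the exemplar" product information. It then gives the source and the place where they are set out: "Summary of Product Characteristics, sections 4.8 of Dermovate ointment and Elocon ointment, and are detailed in this protocol section 11.4".
- **Section 11.4** opens its list with "In the PEARLS trial these targeted AEs are" and then gives the items, with no sign that they are only examples. Sites are told to report these events through the e-CRFs.
- **Section 11** sets the collection rule: "only those AEs which are directly referred to in the e-CRF will be collected for this trial". All AEs go in the medical notes, and any AE that meets the SAE criteria goes on an SAE form whether or not it is listed.

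Safety over 24 months is secondary objective 3 (section 3.3). Section 10.6 reports it as counts and percentages by group.

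**The concern.** Section 11.1 makes two statements about the known reactions: they will be on the e-CRFs, and section 11.4 sets them out. The second is not true of the 11.4 list. The first then depends on which text the e-CRF was built from.

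Section 11 says the targeted complications are recorded in the e-CRFs in structured form, and section 4.4 makes targeted adverse events a safety endpoint. A database designer would therefore naturally take the checklist from 11.4. On that path, a non-serious case of a reaction missing from 11.4 is written in the notes and does not reach the trial data. The loss occurs at collection, so no analysis plan can repair it. Section 2.6 itself remarks that the evidence for quantifying these risks is thin, so incomplete collection would weaken the trial where it could contribute something new.

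**Working it through.** No sample size or power figure is involved. The check compares the list in section 2.6 with the list in section 11.4, term by term, and allows obvious differences in wording (atrophy and atrophic changes, for example).

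| Reaction in 2.6 | Item in 11.4 | Named? |
|---|---|---|
| Infection | Infection item | Yes |
| Burning sensation | Local burning/pain/pruritus item | Yes |
| Pruritus | Same item | Yes |
| Application site pain | Same item (skin pain) | Yes |
| Contact dermatitis | Dermatitis and atrophy item | Yes |
| Skin atrophy | Same item (atrophic changes) | Yes |
| Skin striae | Same item | Yes |
| Folliculitis | None by name; arguably the infection item | No |
| Paraesthesia | None by name; arguably burning | No |
| Acneiform dermatitis | None by name; arguably rash | No |
| Skin hypopigmentation | None | No |
| Hypertrichosis | None | No |

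**By name.** Seven are matched and 12 − 7 = 5 are not; 5/12 = 42%.

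**With generous filing.** The infection item reads "Infection (thrush and superficial bacterial infection"), which could take folliculitis. Paraesthesia could be filed under burning, although it is a different sensation. Acneiform dermatitis could be filed under rash, which appears in two items. Allowing all three leaves 5 − 3 = 2 unplaced, or 2/12 = 17%. If the paraesthesia match is refused, three remain (3/12 = 25%). No reading brings the gap to zero.

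**What follows for the data.** The section 11 rule refers to the e-CRF, not to 11.4, so there are two cases:

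1. *The e-CRF follows 11.4.* Non-serious cases of the unplaced reactions are not trial data, which contradicts the statement in 11.1 that they will be collated.
2. *The e-CRF lists all the known reactions.* The data are collected, but 11.4 then misstates the targeted list.

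The text needs correcting in both cases. Data are lost only in the first.

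**The case against.** The strongest reply is that nothing shown proves any reaction will be missed. The collection rule depends on an e-CRF that is not available, and 11.1 says the known side effects will be on it. That stands. A reader might infer that the five reactions will never be collected, or that their recorded count must be zero; the documents do not support either as a certainty.

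Other safeguards also stand. Serious cases are reported on SAE forms. Expectedness is judged against the product information, not against 11.4 (section 11.5). A reaction requiring cessation of the steroid is a named category in section 11.5, and change or cessation of therapy is recorded at every follow-up visit (Table 7). None of these gives by-arm counts of non-serious reactions that do not lead to a change of treatment.

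A reader might also infer that an excess in the proactive arm would be understated. Exposure does point that way under the planning figures. Assume 4 and 3 flares a year (section 10.1), daily use in a flare, and twice-weekly proactive use otherwise. With 7-day flares, yearly applications are 4 × 7 = 28 reactive and 3 × 7 + (365 − 21)/7 × 2 ≈ 119 proactive. With 30-day flares they are 4 × 30 = 120 and 3 × 30 + (365 − 90)/7 × 2 ≈ 169. But the protocol gives no reaction rates and no link from exposure to rate, and it defines no total of steroid-attributable events that could be biased. The inference remains a possibility without a size.

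Finally, targeted collection is a declared choice, and 11.1 could instead be reworded to call 11.4 a selection. That would remove the contradiction, but only by dropping the commitment to collate the known reactions.

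**Conclusion.** The mismatch is established from the protocol's own text: 11.1 misdescribes 11.4. Five of the twelve reactions in 2.6 are absent by name, and two, skin hypopigmentation and hypertrichosis, are absent on the most generous reading. These are shares of listed terms, not of events.

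The consequence is conditional. If the e-CRF follows 11.4, non-serious cases of the unplaced reactions would be missing from the by-arm safety counts for objective 3. How many cases that is, and whether it would alter the comparison between arms, cannot be estimated from the documents. The product information was not available, so only the protocol's own lists were compared. The point is still worth correcting, because data not collected cannot be recovered at analysis and the repair is small.

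**What to change.** Reconcile sections 2.6, 11.1 and 11.4 and the e-CRF checklist:

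- Add the unplaced terms, at least hypertrichosis and skin hypopigmentation, to the 11.4 list and to the e-CRF.
- For folliculitis, paraesthesia and acneiform dermatitis, either add them too or state in 11.4 and the e-CRF guidance which existing item each is recorded under, so that sites code them alike.
- Check the e-CRF against the revised list. If it already carries all twelve terms, only the protocol text needs changing.

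The cost is at most five more tick boxes on an adverse-event form already completed at every follow-up visit, and a few more non-serious events to record. Hypopigmentation is the awkward item. Whitening is a feature of lichen sclerosus itself (section 1.1), section 11 excludes signs of the disease under study unless more severe than expected, and the site staff making the judgement are not blinded (Table 4). Its counts should be interpreted with caution.
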